5.9.3 Final Product Disposition

The used applicators will be destroyed by the site. For unused malfunctioning applicators, the assigned site personnel will record the nature of the malfunction on the appropriate form. The malfunctioning applicators will be destroyed by the site. All unused applicators will be returned for destruction according to Allergan instructions.

5.9.4 Operative Procedure

The study treatment procedure must be performed only in an operating room, surgical suite, or in an office setting using a sterile technique, as described in the Procedure Manual. The study treatment kit(s) should be readily available during the procedure.

Prior to study treatment, the SE of each patient will be anesthetized with topical and/or subconjunctival anesthetic and prepared according to the investigator's standard of practice. Patients randomized to active treatment will have the study drug placed into the vitreous through the pars plana using the DEX PS DDS. See the Procedure Manual for further details.

Once the DEX PS DDS is deployed, the lever becomes locked to indicate that the applicator has been used and prevents reuse.

6. Response Measures and Summary of Data Collection Methods

6.1 Efficacy Measures

6.1.1 Primary Efficacy Measure

The primary efficacy measure will be BCVA measured by ETDRS.

6.1.2 Secondary Efficacy Measures

Secondary efficacy measures will be:

- central retinal thickness measured by OCT
- total area of macular leakage measured on FA

[REDACTED]

[REDACTED]

[REDACTED]

[REDACTED]

[REDACTED]

[REDACTED]

[REDACTED]

[REDACTED]

[REDACTED]

[REDACTED]

[REDACTED]

[REDACTED]

[REDACTED]

[REDACTED]

6.4 Examination Procedures, Tests, Equipment, and Techniques

6.4.1 Best-corrected Visual Acuity

BCVA in the SE and in the nonstudy eye will be measured using the ETDRS VA protocol following manifest refraction. All BCVA data will be used to assess safety as well as efficacy.

6.4.2 Optical Coherence Tomography

OCT is a laser-based, noninvasive, diagnostic system providing high-resolution imaging optical sections of the retina. The mean retinal thickness in the 1-mm central subfield of the SE will be captured using time-domain OCT (Stratus III, Zeiss) or spectral-domain OCT (Cirrus, Zeiss or Spectralis, Heidelberg). Electronic OCT images will be collected for evaluation by a reading center. Once an OCT instrument has been selected for a patient, that instrument must be used for all the study assessments for that patient for the duration of the study.

6.4.3 Fluorescein Angiography

Early and transit images will be taken of the SE. Mid- and late-phase images will be taken of the study and nonstudy eye. Electronic FA images will be collected for evaluation by a reading center.

6.4.4 Intraocular Pressure Measurement

IOP will be measured using a Goldmann applanation tonometer instrument or a hand held tonometer. Once an instrument for IOP measurement has been selected for a patient, that instrument must be used for all the study assessments for that patient for the duration of the study.

6.5 Other Study Supplies

Laboratory kits for the collection and shipment of hematology, biochemistry, and urine samples, including pregnancy test kits, will be provided by the central laboratory contracted by Allergan.

6.6 Summary of Methods of Data Collection

An IVRS/TWRS will be used to screen, randomize, and manage study medication inventory.

Data will be collected using electronic case report form (eCRF) via a validated electronic data capture (EDC) system. Source documents will be used and stored at sites, and may include a patient's medical records, hospital charts, clinical charts, patient chart, copy of the EDC file, as well as the results of diagnostic tests, such as laboratory tests and ophthalmic examinations or tests. A central lab will be used for the analysis of all blood samples. A central reading facility will be used for FA and OCT evaluations.

7. Statistical Procedures

One database lock will occur when all patients have either completed the study or discontinued from the study prematurely. The study will be unmasked for statistical analysis following the database lock. A detailed analysis plan will be approved prior to database lock.

7.1 Analysis Populations

Three analysis populations will be used for statistical analyses: modified intent-to-treat (mITT), per-protocol (PP), and safety.

The mITT population will include all randomized and treated patients with at least 1 postbaseline BCVA measurement. The mITT population will be used for analysis of efficacy variables and baseline characteristics based on the randomized treatment group.

The PP population will include all randomized and treated patients without any significant protocol violations. The PP population will be used to analyze the primary efficacy variable as a secondary efficacy analysis. The PP analysis will be based on the actual treatment that the patients received.

The safety population will include all treated patients. This population will be used for the safety analysis that will be based on the actual treatment that the patients received.

7.2 Collection and Derivation of Primary and Secondary Efficacy Assessments

BCVA measured in the SE using the ETDRS method will be the primary efficacy assessment. For each patient, BCVA data will be collected for both the study and nonstudy eyes at the

screening, day 1/randomization day (prior to the study treatment), and months 1, 2, 3, 5, 6, 7, 9, 10, and 12/exit (or early exit) visits. Analysis of BCVA obtained from the SE will be performed for efficacy. BCVA data from the nonstudy eye will be used only for safety evaluations.

VA will be recorded on the CRF as the number of letters correctly read. For a given eye, the 4-meter distance (standard) of VA will be tested first. If the patient correctly reads at least 20 letters at 4 meters, the VA score will be set as the sum of 30, and the number of letters read correctly. If the patient correctly reads less than 20 letters at 4 meters, the VA will be measured again at 1 meter. The VA score will be set to the number of letters read correctly at 1 meter plus the number of letters read correctly at 4 meters.

BCVA measured at the randomization visit on day 1 prior to the study treatment will be considered as baseline for change from baseline. BCVA data measured at the screening visit will be used for baseline only in the absence of BCVA data at the randomization visit on day 1.

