2.2 Clinical Hypotheses

- Treatment with 700 µg DEX PS DDS every 5 months is superior to laser photocoagulation according to the modified ETDRS protocol (with respect to the average change from baseline of BCVA during 12 months of treatment for DME)
- 700 µg DEX PS DDS administered every 5 months has an acceptable safety profile

3. Study Design

This study is a multicenter, randomized, 12-month comparative study to evaluate if 700 µg DEX PS DDS administered every 5 months is safe and can achieve improvement of BCVA superior to laser photocoagulation administered according to the modified ETDRS protocol (Section 12.1.11).

Consenting patients will participate in a screening period lasting 2 to 14 days to evaluate patient eligibility. After eligibility has been determined by the investigator, patients will be randomized in a 1:1 ratio to receive:

- 700 µg DEX PS DDS every 5 months
or
- laser photocoagulation according to the modified ETDRS protocol

The randomization will be stratified by BCVA score at baseline (≥ 34 to ≤ 49 and ≥ 50 to ≤ 70) within each investigator site. The primary efficacy measure is average change of BCVA over a period of 12 months. The total duration of study participation for each patient is approximately 12.5 months including screening and randomization/retreatment period. Patients will attend the following 11 visits: screening visit, randomization visit, 8 assessment/retreatment visits, and study exit visit.

4. Study Population and Entry Criteria

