4.1 Number of Patients

Approximately 356 patients will be enrolled at approximately 20 sites to ensure that at least 151 patients in each treatment group complete the study. Of those, approximately 10 patients assigned to DEX PS DDS at selected sites will participate in therapeutic drug monitoring.

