5.5 Treatment Allocation Ratio and Stratification

Patients will be randomized in a 1:1 ratio to either 700 µg DEX PS DDS or laser photocoagulation.

The randomization will be stratified by BCVA score at baseline (≥ 34 to ≤ 49 and ≥ 50 to ≤ 70) within each study site.

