7.3.1 Primary Efficacy Analyses

The primary efficacy endpoint is the average change from baseline in BCVA in 12 months. The primary analysis will be an analysis of covariance (ANCOVA) comparing the treatment difference in the mean average BCVA change from baseline over a 12-month study period. The ANCOVA model will include the treatment group as the main effect and baseline BCVA score as the covariate.

The null hypothesis is that there is no difference between 700-µg DEX PS DDS and laser in the average BCVA change from baseline in a 12-month period. The alternative hypothesis is that there exists a difference between the 2 treatment groups. The hypothesis test will be based on a 2-sided test at 0.05 significance level. In addition, a 2-sided 95% confidence interval (CI) will be constructed for the difference between the treatment groups in least-square means using the same ANCOVA model. Data collected after receiving any prohibited or standard of care treatments will be excluded from all the efficacy analysis.

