2.3 Data Conventions

- Unless stated otherwise in specific subsequent sections, data conventions and definitions listed below will be applied to all analyses. Study duration will be calculated for each participant as:

Study duration = date of the last visit – date of the 1st study treatment + 1

- In general, study day of a visit/assessment/treatment/event/procedure (i.e., BCVA assessment, escape therapy) will be calculated as below.

If the visit date is on or after the 1st study treatment, study day will be calculated as:

Study Day = visit date – date of the 1st study treatment + 1

Day 1 is the day of the 1st study treatment

If visit date is before the 1st study treatment, study day will be calculated as:

Study Day = visit date – date of the 1st study treatment

Day -1 is the day before the 1st study treatment

- Unless otherwise specified, baseline data refer to assessments performed at the Baseline (Day 1) visit prior to the first treatment. Screening or unscheduled but prior to Day 1 visits can be used for baseline in the absence of pertinent data at the baseline visit.
- For continuous variables, descriptive statistics will include mean, median, standard deviation, 25-percentile, 75-percentile, minimum and maximum. Descriptive summary for the categorical data will be count and percentage for each category.
- The Medical Dictionary for Regulatory Activities (MedDRA) nomenclature will be used to code adverse events, biomicroscopy, and ophthalmoscopy findings.
- The Anatomical-Therapeutic-Chemical classification text from World Health Organization (WHO) Drug Dictionary will be used to code all medications for drug class and for drug name.
- All data will be listed.

700 µg DEX PS DDS

- Data after the escape therapy will be excluded from efficacy analyses and will be included in safety analyses. Since assessments (e.g., BCVA, CRT) are usually performed before any treatments (e.g., study treatment, escape therapy), data collected on the same day but prior to the escape therapy will be included in analysis.
- Due to IP recall during the study, a small number of participants have delayed Ozurdex treatment at Month 12. It is recommended that these participants can come back 2 months after the last treatment for a follow-up visit. Therefore, data collected up to day 450 will be used in efficacy analysis. However, all data during the study will be included in safety analysis.

3. Disposition and Exit Status

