5.1.2 Primary Efficacy Analysis

The primary analysis will be an analysis of covariance (ANCOVA) comparing the treatment difference in the mean average BCVA change from baseline over a 12-month study period. The ANCOVA model will include the treatment group as the main effect and baseline BCVA score as the covariate.

The null hypothesis is that there is no difference between 700-µg DEX PS DDS and laser in the average BCVA change from baseline in a 12-month period. The alternative hypothesis is that there exists a difference between the 2 treatment groups. The hypothesis test will be based on a 2-sided test at 0.05 significance level. In addition, a 2-sided 95% confidence interval (CI) will be constructed for the difference between the treatment groups in least-square means using the same ANCOVA model.

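### The primary ANCOVA adjusts for Day 1 BCVA alone; adding the screening BCVA as a second covariate is a cheap improvement likely to sharpen the treatment effect modestly

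*Protocol*

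**What the plan says.** Protocol 7.2 lists the BCVA visits as "screening, day 1/randomization day (prior to the study treatment), and months 1, 2, 3, 5, 6, 7, 9, 10, and 12/exit". Protocol Section 3 sets the gap between the first two: "Consenting patients will participate in a screening period lasting 2 to 14 days to evaluate patient eligibility". Day 1 is the baseline. On the earlier reading, protocol 7.2 says "BCVA data measured at the screening visit will be used for baseline only in the absence of BCVA data at the randomization visit", and SAP 2.3 gives the same fallback: "Screening or unscheduled but prior to Day 1 visits can be used for baseline in the absence of pertinent data at the baseline visit".

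The primary model is the same in protocol 7.3.1 and SAP 5.1.2: "The ANCOVA model will include the treatment group as the main effect and baseline BCVA score as the covariate". The outcome is the time-averaged BCVA by the trapezoidal rule minus baseline (SAP 5.1.1). No visible section uses screening BCVA as a covariate.

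**The concern.** BCVA is a count of letters read, so a single reading differs from the eye's underlying acuity by some error. An ANCOVA that adjusts for one noisy reading removes less of the between-patient variation than one that adjusts for two readings of the same eye taken days apart. The stratification bands span 34 to 70 letters. Over a restricted range, reading error is a larger share of the baseline variance, and a second reading is then most useful.

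What is at stake is precision only: the width of the confidence interval for the primary treatment difference. The screening value is already collected. It precedes randomisation, so adjusting for it cannot introduce bias, and the endpoint, hypothesis and baseline definition are untouched.

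**Working it through.** **Inputs from the documents.** Allocation is 1:1 (protocol 5.5), the test is two-sided at 0.05 (protocol 7.3.1), and the sample size is: "Approximately 356 patients will be enrolled at approximately 20 sites to ensure that at least 151 patients in each treatment group complete the study". The effect size, SD, power and dropout rate are not visible in the public text, so 151 per group cannot be re-derived. The two stated figures fit together if dropout is 15%: 151/0.85 = 177.6, so 178 per group and 356 in total. The 15% is inferred from those same figures (1 − 302/356 = 15.2%).

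**Formula.** Let S be screening BCVA, D Day 1 BCVA and Y the 12-month average. The variance of the treatment effect is proportional to 1 − R². Once D is in the model, analysing Y or Y − D gives the same treatment effect and standard error (SE).

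- One covariate: R² = rDY²
- Two covariates: R² = (rDY² + rSY² − 2·rDY·rSY·rSD)/(1 − rSD²)
- Cost of the extra covariate: multiply the variance by (N − 4)/(N − 5)

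**Check 1: correlations, N = 302 (completers only).** All correlations are assumed.

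- Worked case, rSD = 0.90 and rDY = rSY = 0.60. R² rises from 0.36 to 2(0.36)/1.90 = 0.379. The variance ratio is (0.621/0.640) × (298/297) = 0.974, so the SE falls 1.3%. That is worth 302 × (1 − 0.974), about 8 patients.
- Mid-range, rSD 0.85 to 0.90, rDY 0.5 to 0.7, both readings equally prognostic: the SE falls 0.7% to 3.8%, worth about 4 to 23 patients. A power of 80% would become 80.6% to 83.0%.
- Same range, with screening 5% less correlated with outcome than Day 1: the SE falls 0.05% to 1.6%.
- Screening adds nothing beyond Day 1 (rSY = rSD × rDY): the SE is multiplied by √(298/297), a rise of 0.17%, about one patient.
- Break-even partial r² is 1/298 = 0.0034.

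In simulation at rSD 0.90 and rDY 0.60, the two-covariate SE was the smaller one in 95% of trials with rSY = 0.60, in 58% with rSY = 0.57, and in 21% with rSY = 0.54 (no added information).

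**Check 2: letters, N = 356.** Assumptions: true pre-treatment acuity has mean 56 and SD 14, both readings lie within 34 to 70, visits fall on the planned days, and the average follows the SAP trapezoid. With independent reading errors and true change unrelated to baseline, the variance of the treatment effect falls by:

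| Reading-error SD (letters) | Change SD 7 | Change SD 9 |
|---|---|---|
| 2 | 3.1% | 1.9% |
| 3 | 6.2% | 4.0% |
| 4 | 9.1% | 5.9% |
| 5 | 11.1% | 7.6% |

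In extra patients, 356 × (1/(1 − 0.019) − 1) is about 7 and 356 × (1/(1 − 0.111) − 1) is about 44. At reading-error SD 4 and change SD 9 the SE goes from about 1.003 to 0.972 letters. For an assumed 3-letter difference, power goes from Φ(3/1.003 − 1.96) = 85% to Φ(3/0.972 − 1.96) = 87%. Mean estimates from the two models differed by at most 0.01 letter.

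**Check 3: relaxing the two favourable conditions.** At reading-error SD 4 and change SD 9, the large-sample reduction is 6.3% under the conditions of check 2. It is about 3.3% if true change falls 0.3 letter per baseline letter, about 3.3% if the two reading errors correlate 0.5, and just under 2% (about 0.9% of the SE) with both. Across the whole grid with both, it is about 0.2% to 3% after the degree-of-freedom cost.

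**The case against.** The strongest reply is that nothing in the plan is wrong. A prespecified ANCOVA on Day 1 BCVA is valid and unbiased, protocol and SAP agree on it, and almost any trial could add a covariate. That stands.

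A reader might also infer that the screening value is thrown away. The documents do not support this: it is the fallback baseline in both documents, and protocol 6.4.1 says all BCVA data serve safety and efficacy. It is simply unused in the primary model when Day 1 is present.

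A reader might take the gain as certain and free. It is neither. The 2% to 11% range depends on independent reading errors and on change unrelated to baseline. Readings 2 to 14 days apart may share a transient fluctuation, and eyes with better acuity have less room to gain. The precision cost is very small but not zero.

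There is also a timing objection. SAP 2.3 already describes a product recall during the study, so the SAP was written late. Investigators know the assignment (protocol 9.4), and changing a primary model for perhaps 1% of the SE could raise questions about motive. This stands as a condition on the fix: the change must be fixed and documented before database lock and unmasking.

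Two points on the other side remain. The 302 in check 1 is conservative, because the mITT population keeps every treated patient with one postbaseline BCVA. And the balance is lopsided: the worst case loses about one patient, while the mid-range with equally prognostic readings gains 4 to 23.

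**Conclusion.** The point holds as a modest efficiency improvement of low severity. The primary analysis is valid as planned; adding screening BCVA is expected to tighten it a little. At 356 patients the variance reduction is about 2% to 11% under favourable assumptions and about 0.2% to 3% under less favourable ones, with a possible SE loss of under 0.2%. The SDs, correlations and slope are all assumed, because the visible documents give none.

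Two stronger conclusions are not supported. The plan does not produce a biased estimate or a wrong type I error. Nor can any shortfall in power be shown, since the basis of the sample size is not visible.

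**What to change.** In SAP 5.1.2, mirrored in protocol 7.3.1, fit the ANCOVA with treatment, Day 1 BCVA and screening BCVA, the last two as continuous covariates. Keep the change relative to Day 1 under the existing baseline rule. If one of the two readings is missing, set it equal to the other. Use the same model for the per-protocol analysis (SAP 5.1.3) and the China subgroup (SAP 8.1). Report the single-covariate model as a sensitivity analysis.

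Date and approve the change before database lock and unmasking, and record it in SAP Section 11.

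The cost is one degree of freedom, a short SAP edit and a matching protocol edit, which goes through the approval route in protocol 10.2. No new visit or data item is needed.

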7.2.1 Primary Efficacy Variables

The primary efficacy variable is the average change from baseline in BCVA over the 12-month study period. The average change will be computed by subtracting the baseline BCVA from the area under the BCVA curve (AUC) divided by the total follow-up time for each patient. Calculations for AUC will be based on observed data using the trapezoidal method and will include all postbaseline BCVA data for the patient from the study treatment to the last VA measurement, regardless of scheduled or unscheduled visits.

7.2.2 Secondary Efficacy Variables

Secondary efficacy variables include: ≥ 15 letters improvement from baseline in BCVA at month 12; change from baseline in the retinal thickness based on OCT at month 12; and change from baseline in total leakage area based on FA at month 12.

Change From Baseline in Retinal Thickness Based on OCT

OCT is a laser-based diagnostic system providing high-resolution optical sections of the retina. OCT will be performed at the investigators' sites. The OCT images will be transferred to the reading center and evaluated by the retina specialists of the reading center

700 µg DEX PS DDS

for the SE. The retinal thickness (microns) in the central 1-mm macular subfield based on OCT will be assessed and analyzed as the secondary efficacy variable.

Change From Baseline in Total Leakage Area Based on FA

FA is a technique to examine the circulation of the retina using the dye tracing method. It involves injection of sodium fluorescein into the systemic circulation, and then an angiogram is obtained by photographing the fluorescence emitted after illumination of the retina. The focal and diffuse leakage area based on FA will be assessed. The total leakage area defined as the sum of focal and diffuse leakage area will be computed and analyzed as the secondary efficacy variable.

7.3 Hypothesis and Methods of Analysis

Unless stated otherwise, analyses for efficacy will be performed using the mITT population based on the 2-sided hypothesis test with a nominal significance level of 0.05.

7.3.1 Primary Efficacy Analyses

The primary efficacy endpoint is the average change from baseline in BCVA in 12 months. The primary analysis will be an analysis of covariance (ANCOVA) comparing the treatment difference in the mean average BCVA change from baseline over a 12-month study period. The ANCOVA model will include the treatment group as the main effect and baseline BCVA score as the covariate.

The null hypothesis is that there is no difference between 700-µg DEX PS DDS and laser in the average BCVA change from baseline in a 12-month period. The alternative hypothesis is that there exists a difference between the 2 treatment groups. The hypothesis test will be based on a 2-sided test at 0.05 significance level. In addition, a 2-sided 95% confidence interval (CI) will be constructed for the difference between the treatment groups in least-square means using the same ANCOVA model. Data collected after receiving any prohibited or standard of care treatments will be excluded from all the efficacy analysis.

